10.4.5.7 Other Variables Related to Safety

Other safety variables include the SAS, the BARS, the AIMS, and the C-SSRS.

These scales will be summarized by treatment group and visit including, where appropriate, change from Baseline measures.

Confidential Page 85 of 102

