- 7. Risk for suicidal behavior during the study as determined by the Investigator's clinical assessment and Columbia-Suicide Severity Rating Scale (C-SSRS) as confirmed by the following: answers "Yes" on items 4 or 5 (C-SSRS Ideation) with the most recent episode occurring within the 6 months before Screening, or answers "Yes" to any of the 5 items (C-SSRS Suicidal Behavior) with an episode occurring within the 12 months before Screening. This assessment will be repeated at Baseline Visit (at baseline "Since Last Visit" version of the CSSR-S scale should be used). Non-suicidal self-injurious behavior is not exclusionary.
- 8. Risk of violent or destructive behavior based on the Investigator's opinion and homicidal ideation based on responses to SCI-PANSS interview questions or statements made by the patient at any other times during the Screening or Baseline visits.
- 9. Patients with clinically significant tardive dyskinesia determined by a score of ≥3 on Item 8 of the AIMS at Screening.
- 10. Patients with a score of ≥ 3 on the BARS global clinical assessment of akathisia at Screening.

Medical History and Concurrent Diseases

Confidential Page 39 of 102

- 11. Patients who met DSM-5 criteria for substance abuse or dependence within the past 1 year, including alcohol and benzodiazepines, but excluding caffeine and nicotine. Previous occasional use of alcohol or cannabis is allowed as long as the level of use does not meet DSM-5 criteria for any moderate or severe substance use disorder within the 12 months prior to Screening, and the use of alcohol or cannabis is not considered to be the precipitating factor of the current psychotic episode in the opinion of the Investigator; subjects are required to abstain from alcohol and cannabis use during the trial.
- 12. Patients with hypothyroidism or hyperthyroidism (unless condition had been stabilized with medications for at least the past 90 days) and/or clinically significant abnormal thyroid function (abnormal TSH levels followed by free T3 and T4 levels), as assessed by the Investigator, in discussion with the study Medical Monitor.

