### 5.2.13 Columbia-Suicide Severity Rating Scale (C-SSRS)

The following outcomes are C-SSRS categories and have binary responses (yes / no). The categories have been re-ordered from the actual scale to facilitate the definition of composite endpoints:

Category 1	Wish to be Dead
Category 2	Non-specific Active Suicidal Thoughts
Category 3	Active Suicidal Ideation with Any Methods (Not Plan) without Intent to Act
Category 4	Active Suicidal Ideation with Some Intent to Act, without Specific Plan
Category 5	Active Suicidal Ideation with Specific Plan and Intent

Category 6	Preparatory Acts or Behavior
Category 7	Aborted Attempt
Category 8	Interrupted Attempt
Category 9	Actual Attempt (non-fatal)
Category 10	Completed Suicide

Suicidal Ideation since baseline – A “yes” answer at any time during double blind treatment to any one of the 5 suicidal ideation questions (categories 1-5) on the C-SSRS.

Suicidal Behavior since baseline – A “yes” answer at any time during double blind treatment to any one of the 5 suicidal behavior questions (categories 6-10) on the C-SSRS.

There will be no imputation of missing data for C-SSRS.

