#### **5.13.7    C-SSRS**

Suicidal ideation and suicidal behavior as measured by the C-SSRS will be summarized using frequencies and percentages by treatment group and timepoint. All C-SSRS data will also be listed.

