### **5.13.8 Simpson-Angus Scale (SAS)**

Observed and change from Baseline values for the SAS will be provided by treatment group. Total scores as well as individual question responses and scores will be listed.

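### The SAP's suicidal ideation 'since baseline' makes no comparison with Baseline, so continuing or recurring entry ideation is counted together with new or worsened ideation

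*Protocol*

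**What the plan says.** SAP 5.2.13 orders the C-SSRS items as categories 1 to 10 and defines two outcomes labelled as since baseline. Ideation is a yes "answer at any time during double blind treatment to any one of the 5 suicidal ideation questions (categories 1-5) on the C-SSRS". Behavior is a yes "answer at any time during double blind treatment to any one of the 5 suicidal behavior questions (categories 6-10) on the C-SSRS". Neither definition refers to what the patient reported before the first dose.

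The analysis in SAP 5.13.7 is one sentence plus a listing: "Suicidal ideation and suicidal behavior as measured by the C-SSRS will be summarized using frequencies and percentages by treatment group and timepoint". The SAP's table list has a single C-SSRS table, 14.3.7.10.

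The protocol groups the C-SSRS with the SAS, BARS and AIMS in section 10.4.5.7: "These scales will be summarized by treatment group and visit including, where appropriate, change from Baseline measures".

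At entry, exclusion 7 (Protocol 5.2) is item-based for ideation items 4 and 5, "with the most recent episode occurring within the 6 months before Screening", and for any suicidal behavior item within 12 months. Items 1 to 3 are not excluded by item, although the Investigator's judgment can remove some of these patients. The Baseline/Screening form is used at Screening, and the since-last-visit form at Day 1 and every later visit (Protocol 7.1 footnotes and 8.2.9).

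**The concern.** The safety question is whether suicidality appears or worsens on LB-102. An outcome named as since baseline should answer it, but this one cannot separate a patient whose passive ideation is unchanged from one whose ideation is new or has escalated.

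Elsewhere the SAP does use the pre-treatment state. Its treatment-emergent adverse event definition (5.13.1) covers worsening of a pre-existing condition. Shift tables are planned for laboratory data, ECG interpretation and physical examination (5.13.2, 5.13.4, 5.13.5). The three movement scales keep change from Baseline (5.13.8 to 5.13.10), for example "Observed and change from Baseline values for the SAS will be provided by treatment group". The C-SSRS has no equivalent.

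Safety is a secondary objective and the C-SSRS a listed safety endpoint. Protocol 1.1 describes a population with ten times the general suicide risk. A reader of the study report would look to this table first, and as planned it mixes background with signal.

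**Working it through.** **What the planned count does with typical patients**

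| Pre-dose ideation | Worst on treatment | Planned 'since baseline' count | What happened |
|---|---|---|---|
| none | category 1 | event | new |
| category 1 | category 1 | event | continued |
| category 1 | category 3 | event | worsened |
| category 3 at Screening, none at Day 1 | none | no event | resolved |
| category 3 at Screening, none at Day 1 | category 3 | event | recurred |

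Rows 1, 2, 3 and 5 are indistinguishable in the outcome. Row 4 is correctly left out, because the form used on treatment asks only about the time since the previous visit.

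**Size of the attenuation**

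The documents state no C-SSRS rate, so there is no figure of the plan to reproduce, and every input below is assumed. Let *b* be the share entering with ideation, *r* the share of these who stay positive on treatment (taken as equal across arms), and *p* the new-onset rate in the rest.

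P(any yes) = b·r + (1 − b)·p

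Difference between arms = (1 − b)(p_LB − p_pbo), since b·r cancels.

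Ratio = [b·r + (1 − b)p_LB] / [b·r + (1 − b)p_pbo], which moves towards 1 as b·r grows.

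For new onset of 3% on placebo and 6% on LB-102 (ratio 2.00, difference 3.0 points among patients free of ideation at entry):

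| b | r | Placebo | LB-102 | Ratio | Difference (points) |
|---|---|---|---|---|---|
| 0 | any | 3.0% | 6.0% | 2.00 | 3.0 |
| 5% | 50% | 2.5 + 2.85 = 5.35% | 2.5 + 5.7 = 8.2% | 1.53 | 2.85 |
| 10% | 50% | 5 + 2.7 = 7.7% | 5 + 5.4 = 10.4% | 1.35 | 2.7 |
| 20% | 80% | 16 + 2.4 = 18.4% | 16 + 4.8 = 20.8% | 1.13 | 2.4 |
| 30% | 80% | 24 + 2.1 = 26.1% | 24 + 4.2 = 28.2% | 1.08 | 2.1 |

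For 5% versus 10% (ratio also 2.00), the count gives 7.25% versus 12.0%, ratio 1.66, at b = 5% and r = 50%. It gives 27.5% versus 31.0%, ratio 1.13, at b = 30% and r = 80%.

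The difference shrinks only by the factor 1 − b, and the ratio shrinks more. On the difference scale the main losses are the added background and escalation among patients who entered with ideation: that escalation contributes nothing to the contrast, because those who stay positive already count as events.

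**Behavior**

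Any behavior within 12 months before Screening is exclusionary, so little can carry over from entry into categories 6 to 10.

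**The case against.** The strongest reply has five parts.

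- **Protocol.** A reader might infer that the SAP drops a change from Baseline that the protocol requires, and that SAP Section 8 should have declared it. The text does not support this. Protocol 10.4.5.7 asks for change only where it suits the measure, and a numeric change does not suit yes/no items. This part of the reply stands in full.
- **Form.** Only ideation that continues or recurs after dosing can be counted, and the Investigator may exclude some at-risk patients beyond items 4 and 5. This stands, and it limits the number affected without removing the problem.
- **Table shells.** They are a separate document, and Table 14.3.7.10 may carry category rows and a Baseline column. If so, an on-treatment category 4 or 5 would mostly be escalation, because recent items 4 and 5 are excluded at entry. Such rows would still be frequencies per visit. They would not separate new from continuing ideation in categories 1 to 3, nor show a move within that range.
- **Adverse events and listings.** Worsening reported as an adverse event would be tabulated by arm with a relative risk (SAP 5.13.1), and all C-SSRS data are listed. These help, but one depends on spontaneous or general questioning and the other on reconstruction by hand. Neither is a prespecified summary of the systematic instrument.
- **No inference.** No test or effect estimate is planned for the C-SSRS, and randomization balances entry ideation on average. This stands, and the point must be worded as attenuation of a description.

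**Conclusion.** The definition does not do what its label says. Continuing or recurring ideation in categories 1 to 3 is counted with new or worsened ideation, and the planned summary is not specified to show escalation within a patient. That follows from the text alone.

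The consequence is attenuation, conditional on some patients entering with ideation that persists. If none do, there is none. In the 3% versus 6% illustration a ratio of 2.00 falls to between 1.53 and 1.08, and a difference of 3.0 points to between 2.85 and 2.1. These figures rest on assumed prevalence, persistence and onset rates and on equal persistence in all arms, so they show a range and not an estimate for this trial.

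A reader might go further and conclude that the safety comparison is biased in favor of LB-102 or is known to be diluted. The documents do not support either. Entry ideation is a pre-randomization characteristic, its frequency is not given, and the summary is descriptive. The effect on behavior is small. This is a worthwhile, inexpensive improvement to a safety summary, not an error that threatens the trial's conclusions.

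**What to change.** In SAP 5.2.13 and 5.13.7, using the category ordering already defined there:

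1. Add treatment-emergent ideation and treatment-emergent behavior: a highest on-treatment category above the highest pre-dose category, assessed within categories 1 to 5 and 6 to 10 respectively, reported by arm.
2. Add to Table 14.3.7.10 a shift table by arm of pre-dose category against worst on-treatment category.
3. Prespecify the pre-dose reference and show both versions: Day 1 alone (since-last-visit form), and Day 1 plus the recent period recorded at Screening. With a long look-back alone, a patient with category 3 before entry, none at Day 1 and category 3 again on drug would not count as emergent. With Day 1 alone that recurrence does count.
4. Keep the any-yes count and the by-timepoint frequencies.

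The C-SSRS is already collected at Screening and Day 1, so no new data are needed. The cost is SAP wording and a few table rows, many of which will hold small counts. The summary stays descriptive.

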10.4.6 Pharmacokinetics

Data from patients who participated in the study will be included in the PK analysis. Patients with missing sample concentrations will be included in the PK analyses, provided their PK parameters can be adequately characterized based upon the remaining data.

Deviation from procedures described in this protocol that impact the quality of data required to meet the objectives of the study will be documented and may result in the exclusion of PK data from the analyses for a particular patient. This includes any deviations or events that would invalidate the evaluation of the PK. Examples of deviations and events that could result in the exclusion of PK data from the analyses include emesis after dosing (within the predetermined time), sample processing, or assay errors that lead to inaccurate bioanalytical results. Other deviations or events that do not disqualify data from analyses may require minor adjustments to calculations. If these occur, data analyses will be adjusted and documented accordingly such that conclusions are not biased. An example of such an event includes, but is not limited to, minor deviations between the actual and scheduled time of sample collection.

Other PK analyses may be performed as appropriate.

Plasma concentrations of LB-102 will be measured during the study and PK parameters derived using noncompartmental or compartmental methods as appropriate. The following PK parameters (as appropriate) will be calculated: AUC_{0-t} , AUC_{0-24} , AUC_{0-inf}

No value for λ_z , AUC_{0-inf}, CL/F, or $t_{1/2}$ will be reported for cases that do not exhibit a terminal log-linear phase in the concentration versus time profile.

No PK parameters will be calculated for patients with no detectable concentrations for 2 or fewer time points.

Individual and mean plasma concentration-time curves (both linear and log-linear) will be included in the final report.

PK parameters of LB-102 and metabolites will be summarized by cohort using descriptive statistics

Figures will be created to display mean and individual patient LB-102 and concentration-time curves in plasma on both a linear and logarithmic scale. Dose proportionality will be assessed using linear regression, or another acceptable approach.

10.4.7 Interim Analysis

No interim analysis is planned for this study.

Confidential Page 86 of 102

11 STUDY MANAGEMENT AND RESPONSIBILITIES

11.1 Ethics

11.1.1 Good Clinical Practice

The study will be performed in accordance with this protocol, local national laws (as applicable), ICH guideline for Good Clinical Practice (GCP),³ and the most recent guidelines of the Declaration of Helsinki.⁷

11.1.2 Institutional Review Board

Conduct of the study must be approved by an appropriately constituted IRB. Approval is required for the study protocol, IB, protocol amendments, ICFs, patient information sheets, and advertising materials. No study drug will be shipped to a site until written IRB authorization has been received by the Sponsor or its representative.

11.1.3 Informed Consent

For each study patient, a written ICF will be obtained before any protocol-related activities are performed. As part of this procedure, the Investigator or a designated representative must explain orally and in writing the nature, duration, and purpose of the study, and the action of the study drug in such a manner that the patient is aware of the potential risks, inconveniences, or adverse effects that may occur. Patients should be informed that they may withdraw from the study at any time. They will receive all information that is required by local regulations and ICH guidelines. The PI or a designated representative will provide the Sponsor or its representative with a copy of the IRB-approved ICF before the start of the study.

Subjects will also be asked to provide additional consent for their participation in a secure, proprietary research subject database administered by VCT [Verified Clinical Trials, Garden City, NY]. The database will utilize partially identified subject information to review subjects' research study history within the database. Participants who are identified as verification failures by VCT, should not be enrolled without documented approval from LB Pharmaceuticals and Worldwide. At the last subject contact, VCT staff will automatically close out the subject (safety follow-up, ET, or complete) based on the IXRS.

11.1.4 Confidentiality

All information generated in this study is considered highly confidential and must not be disclosed to any person or entity not directly involved with the study unless prior written consent is gained from the Sponsor. However, authorized regulatory officials, IRB personnel, the Sponsor and its authorized representatives are allowed full access to the records.

11.2 Auditing and Monitoring

To ensure accurate, complete, and reliable data, will provide instructional material to the study sites and the Sponsor at a start-up training session to instruct the Investigators and

Confidential Page 87 of 102

study coordinators. This session will give instruction in the protocol, the completion of the eCRFs, and study procedures.

This study will be monitored for quality assurance at all stages of its development by the clinical research personnel employed by the Sponsor or its representative. A Monitoring Plan will be developed and approved by the Sponsor using a risk-based monitoring approach with the primary focus on critical data and processes that if inaccurate, not performed, or performed incorrectly, would threaten the protection of human patients or the integrity of the study results. Monitoring may include remote monitoring, personal visits, and/or telephone communication to assure that the investigation is conducted according to the protocol, SOPs, GCP guidelines, and applicable regulatory requirements. Quality control procedures will be applied to each stage of data handling to ensure that all data are reliable and have been processed correctly. As defined in the Monitoring Plan, eCRFs may be reviewed remotely or on-site for completeness, clarity, and consistency with source documents available for each patient. At the conclusion of the study, will conduct a quality review of the database.

The study may be audited by the Sponsor, and/or regulatory agencies at any time. Investigators will be given a notice before an audit occurs.

Medical advisors and clinical research associates or assistants may request to witness patient evaluations occurring as part of this protocol. The Investigator and appropriate personnel will be periodically requested to attend meetings/workshops organized by the Sponsor to assure acceptable protocol execution. The study may be subject to audit by the Sponsor or by regulatory authorities. If such an audit occurs, the Investigator must agree to allow access to required patient records. By signing this protocol, the Investigator grants permission to personnel from the Sponsor, its representatives, and appropriate regulatory authorities for on-site monitoring of all appropriate study documentation, as well as on-site review of the procedures employed in the eCRF generation, where clinically appropriate.

11.3 Data Handling, Documentation, and Record Keeping

11.3.1 Source Documentation

Note that a variety of original documents, data, and records for a given patient (e.g., hospital records, clinical and office charts, laboratory notes, memoranda, patient's diaries or evaluation checklists, pharmacy dispensing records, recorded data from automated instruments, copies or transcriptions certified after verification as being accurate copies, microfiches, photographic negatives, microfilm or magnetic media, X-rays, patient files, and records kept at the pharmacy, at the laboratories, and at medico-technical departments involved in the clinical study) will be considered as source documents in this study. All study specific information obtained at each study visit must be recorded in the patient's record (source documentation), and then entered into a validated EDC database by trained site personnel.

11.3.2 Direct Access to Source Data and Documents

The Investigator/institution will provide direct access to source data and documents for trial-related monitoring, audits, IRB, and regulatory inspection.

Confidential Page 88 of 102

11.3.3 Record Retention

The Investigator must arrange for retention of study records at the site. The nature of the records and the duration of the retention period must meet the requirements of the relevant regulatory authority but should not be less than 2 years after the first marketing approval. In addition, the retention period must meet the requirements of the most stringent authority. The Investigator should take measures to prevent accidental or premature destruction of these documents.

11.3.4 Study Documentation

By signing a copy of the country-specific regulatory form(s), the PI or designated representative acknowledges that they have received a copy of the IB on LB-102 and assures the Sponsor that they will comply with the protocol and the provisions stated in the country-specific regulatory form(s). No changes in this protocol can be made without the Sponsor's written approval.

11.4 Indemnification

The Sponsor's indemnification of the Investigator and institution during the conduct of this study is addressed in a letter of indemnification provided as a separate document. Other indemnification or insurance will be provided as necessary under local regulations.

11.5 Amendments

Protocol modifications, except those intended to reduce immediate risk to study patients, may be made only by the Sponsor. A protocol change intended to eliminate an apparent immediate hazard to patients may be implemented immediately, provided the IRB is notified within 5 calendar days.

Any permanent change to the protocol must be handled as a protocol amendment. The written amendment must be submitted to the IRB and the Investigator must await approval before implementing the changes. The Sponsor will submit protocol amendments to the appropriate regulatory authorities for approval.

If in the judgment of the IRB, the Investigator, and/or the Sponsor, the amendment to the protocol substantially changes the study design and/or increases the potential risk to the patient and/or has an impact on the patient's involvement as a study patient, the currently approved written ICF will require similar modification. In such cases, informed consent will be renewed for patients enrolled in the study before continued participation.

11.6 Study Discontinuation

Both the Sponsor and the PI or designated representative reserve the right to terminate the study at the Investigator's site at any time. Should this be necessary, the Sponsor or a specified designee will inform the appropriate regulatory authorities of the termination of the study and the reasons for its termination, and the PI or designated representative will inform the IRB of the same within the required time frame. In terminating the study, the Sponsor and the PI or designated representative will assure that adequate consideration is given to the protection of the patients' interests.

Confidential Page 89 of 102

